## Protocol Synopsis

**Study Title:** A randomised optimisation study of a brief digital imagery-competing task intervention to support NHS ICU staff experiencing intrusive memories of traumatic events from working in the COVID-19 pandemic.

**Short Study Title:** A brief Gameplay Intervention for NHS ICU Staff affected by COVID-19 trauma (GAINS Study)

**Chief Investigator:** [name]

**Study Centre(s):** Study will be completed remotely in locations of participant's choosing with internet accessibility

### **Primary Objective:**

- To determine if immediate access to the intervention plus symptom monitoring for 4 weeks (immediate intervention arm), compared to usual care for 4 weeks (delayed intervention arm), can reduce the number of intrusive memories in week 4 (i.e. between-groups comparison).

### **Secondary Objectives:**

- To determine if access to the intervention plus symptom monitoring for 4 weeks can reduce the number of intrusive memories from run-in week (pre-intervention) to week 4 (post intervention; within-group comparison in the immediate intervention arm) and from week 4 (pre intervention) to week 8 (post intervention; within-group comparison in the delayed intervention arm)
- To determine if immediate access to the intervention plus symptom monitoring for 4 weeks (immediate intervention arm), compared to usual care for 4 weeks (delayed intervention arm), can reduce intrusive memory ratings of distress and disruption to concentration/functioning; symptoms of post-traumatic stress, anxiety, depression and insomnia; sickness absence; burnout; intention to leave job; and improve work engagement, functioning and quality of life at 4 weeks (i.e. between-groups comparison).
- To determine if access to the intervention plus symptom monitoring for 4 weeks can reduce intrusive memory ratings of distress and disruption to concentration/functioning; symptoms of post-traumatic stress, anxiety, depression and insomnia; sickness absence; burnout; intention to leave job; and improve work engagement, functioning and quality of life from baseline (pre intervention) to 4 and 8 weeks (post intervention; within-group comparison in the immediate intervention arm) and from 4 weeks (pre intervention) to 8 weeks (post intervention; within-group comparison in the delayed intervention arm).

### **Tertiary Objectives:**

- To assess support (from managers and from family/friends), new stressful/traumatic events, new treatments, changes to work
- To obtain feasibility data to improve the intervention implementation.
- To assess the acceptability and perceived value of the intervention from participants to optimise the intervention implementation.
- To assess the guidance given by the expert researchers to participants to explain how to use the intervention, in order to identify ways to train non-expert researchers to give guidance.

- To assess the guidance given by both expert and non-expert researchers to identify ways to digitise such guidance to establish a fully self-guided version of the intervention.

**Hypothesis and Brief Rationale:**

The primary hypothesis is that participants in the immediate intervention arm, compared to the delayed intervention arm, will have fewer intrusive memories in week 4 (between-groups comparison).

**Study Design:**

This optimisation study uses a two-arm, parallel-group, randomised controlled trial. The study's randomisation method allocates participants using a 1:1 overall ratio to one of two arms:

Immediate intervention arm = immediate access to the brief digital imagery-competing task intervention plus symptom monitoring for 4 weeks

Delayed intervention arm = usual care for 4 weeks followed by access to the intervention plus symptom monitoring for 4 weeks

**Study Period:**

Each participant will be in the study for a total of up to 17 weeks. There will be virtual visits (i.e., audio or video calls between participant and researcher) at screening, on first intervention day, for optional qualitative interview, and to provide support with additional intervention sessions or assist the participant (e.g., with outcome completion) when appropriate. Remote participant assessments (i.e., typically without researcher; online questionnaires only) will take place at Baseline, 4 and 8 weeks.

Total duration of the study from first participant enrolment to last participant completing the study is expected to last approximately 9 months, but will depend on the number enrolled.

**Number of Participants:**

The study will enrol up to approximately 150 participants, 75 per study arm.

**Main Entry Criteria:****Main Inclusion Criteria:**

- Aged 18 or above.
- Able to read, write and speak in English.
- Worked in a clinical role in an NHS Intensive Care Unit or equivalent during the COVID-19 pandemic (e.g. as a member of ICU staff or deployed to work in the ICU during the pandemic).
- Experienced at least one traumatic event related to their work during the COVID-19 pandemic, meeting criterion A of the Diagnostic and Statistical Manual of Mental Disorders, 5th edition (DSM-5) criteria for Post-Traumatic Stress Disorder (PTSD): "exposure to actual or threatened death, serious injury, or sexual violence" by "directly experiencing the traumatic event(s)" or "witnessing, in person, the event(s) as it occurred to others".
- Experience intrusive memories of the traumatic event(s).
- Experienced at least three intrusive memories in the week prior to screening.
- Have internet access.
- Willing and able to provide informed consent and complete study procedures (including briefly listing their intrusive memories (without going into any detail), and playing the computer game Tetris® with particular mental rotation instructions, and completing an online intrusive memory diary).

- Willing and able to be contacted by the research team during the study period.

**Main Exclusion Criteria:**

Have fewer than three intrusive memories during the run-in week. We will not exclude those undergoing other treatment for PTSD or its symptoms, so the study is as inclusive as possible to meet the challenges ICU staff are facing during the COVID-19 pandemic.

**Study Intervention:**

This brief imagery-competing digital task intervention consists of a brief reminder cue to a specific intrusive memory, followed by playing the computer game Tetris® for 20 minutes with instructions to use mental rotation during game play. The study team will provide a single training session on completing the intervention for the first time (guided session). The intervention can then be repeated for other intrusive memories. Participants will learn to complete the intervention in the initial guided session with the help of a researcher, and thereafter use it self-guided for other existing intrusive memories or if intrusive memories from a new trauma arise (with the option for researcher support). The intrusive memory diary (based on e.g., Holmes et al., 2009; Iyadurai et al., 2018; Kanstrup, Singh et al., 2021; Kubickova et al., in prep) helps to indicate when they might benefit from repeating the intervention.

**Outline of Study:**

The study is divided into approximately a 1-5 week screening period including one week run-in period to determine eligibility prior to randomisation followed by approximately 8 weeks in the study period and 2 weeks optional, qualitative interview period.

Participants will be recruited through the Intensive Care Society network membership and existing social media followers supplemented by targeted advertisements in social media (e.g. Facebook, Twitter).

Those who are interested in taking part in the study will be asked to complete a brief online eligibility questionnaire anonymously, which can be accessed on the study website. Participants will be asked to give online consent before completing the questionnaire. Those who meet all the inclusion criteria will be asked to provide their contact details (name, telephone number and email address). A researcher will then arrange a time to contact them by phone or video call to obtain informed consent and go through the study inclusion and exclusion criteria.

All participants will be asked to complete a daily online intrusive memory diary for a run-in period of one week to record a simple count of the number of intrusive memories they have each day using a secure web-based clinical research system, P1vital® electronic patient reported outcome (ePRO) system. Those meeting the study eligibility criteria will then be sent a link to complete baseline questionnaires using ePRO. After completing baseline questionnaires, participants will be randomised by ePRO to receive either the immediate intervention arm or the delayed intervention arm using a 1:1 overall ratio. After randomisation, participants will be sent information explaining what will happen next in the study. This information will differ according to whether they have been allocated to the immediate intervention or delayed intervention arm. Note: to minimise expectation bias, participants are not told that the study has two arms or to which arm they have been assigned; participants are informed during the consent process that they will have access to an online intervention for 4 weeks 'at some point' within an 8-week period.

- Participants in the immediate intervention arm will be contacted immediately by a researcher to arrange a video call to go through the brief digital intervention for the first time with researcher support (the guided session: Day 1). The brief digital intervention is a c. 30-minute, single session task completed by the participant on their smart phone or other internet enabled device delivered on a secure web platform

used for clinical self-management of health in general practice (i-spero®). Participants in this arm will have continuous access to the intervention over the next 4 weeks (Day 1-28) and can use the intervention either on their own or with the option of researcher support. As part of the intervention, participants complete a daily record of their intrusive memories in i-spero® to identify which intrusive memories they have had, and therefore which to target with the intervention. In week 4 (Day 22-28), they will be asked to complete a daily intrusive memory diary and intrusive memory rating questionnaire in ePRO (identical to the run-in week) to assess how many intrusive memories they had each day.

- Participants in the delayed intervention arm will be asked to complete the online intrusive memory diary and intrusive memory rating questionnaire using ePRO during week 4 (Day 22 to 28), to assess how many intrusive memories they had each day. The online intrusive memory diary completed during week 4 will be the same as the intrusive memory diary completed by all participants in the run-in week. After these first 4 weeks, they will be contacted by a researcher to arrange a video call to go through the brief digital intervention for the first time (as in the immediate intervention group, i.e. the guided session: Day 29+7 days). Participants in the delayed intervention arm will have continuous access to the intervention over the next 4 weeks (Day 29 to 56+7 days) and can use the intervention either on their own or with the option of researcher support. As part of the intervention, participants complete a daily record of their intrusive memories to identify which intrusive memories they have had, and therefore which to target with the intervention. In week 8 (Day 50 to 56 +7), they will be asked to complete a daily intrusive memory diary and intrusive memory rating in ePRO (identical to the run-in week) to assess how many intrusive memories they had each day.

Participants in both arms will be asked to complete outcome questionnaires using ePRO at 4 weeks (Day 28) and 8 weeks (Day 56). They will also be asked to complete an online feedback questionnaire about their experience of using the intervention and they will be given the option of completing a qualitative interview with a researcher via audio or video call. This will be completed after week 4 (Day 28) for participants in the immediate intervention arm and after week 8 (Day 56+7 days) for participants in the delayed intervention arm.

Note: Day 1 in the immediate intervention group is defined as the day on which the participant completes the first intervention session with researcher support (guided session). The timing of this first intervention session post randomisation may vary slightly from participant to participant in the intervention arm. Day 1 for participants in the delayed intervention arm will be paired to the timing of Day 1 for participants in the immediate intervention arm, so that the timing of the primary outcome assessment post randomisation will be approximately equal between the two groups.

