**Tertiary Endpoint**

- 8-item questionnaire (changes to health and work) at 4 weeks (Day 28) and 8 weeks (Day 56) (both arms).
- Rates of recruitment, intervention use/adherence, outcome measure completion and participant attrition.
- Feedback questionnaire at 4 weeks post first intervention session in both arms (i.e. Day 28 in the immediate intervention arm and Day 56+7 days in the delayed intervention arm).
- Optional qualitative interview at 4 to 6 weeks post first intervention session in both arms (i.e. Day 29+14 days in the immediate intervention arm and Day 57+14 days in the delayed intervention arm).
- Optional qualitative interview information about guidance given by the expert/non expert researchers to help participants to learn how to use the intervention.

Refer to section 5.7 for specific timings of assessments by day.

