#### 5.7.7 Feedback questionnaire

A 12-item questionnaire will assess participants' experience of using the intervention. The first ten items assess how easy, helpful, distressing, burdensome and acceptable participants found the intervention, how willing they would be to use it in the future, how confident they would be in recommending it to a friend and how much they feel it could be used to support staff within NHS ICUs, each rated from 0 (not at all) to 10 (very). The last two items ask how the intervention could be improved, for any other comments or suggestions about the intervention, and for the occurrence of any adverse events, all with an open response.

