**Confidential**

P1V\_GAINS\_IN01 Study Protocol

Record of intrusive memories (daily)					x..x(Imm)				x..x(Del)				
Feedback questionnaire	11							x(Imm)				x(Del)	
Qualitative interview (Optional)									$x^3$				$x^3$
Note: measures in bold are in i-spero; measures not in bold are in ePRO; Del = delayed-intervention arm, Imm = immediate-intervention arm, X = all participants (immediate and delayed intervention arms)													

1. To be completed by participants at the end of the week (7th day)

2. Participant for both arms will have a +7 days window to complete week 4 and week 8 outcome measures.

3. Optional qualitative interview for immediate and delayed intervention arm can be completed within 14 days of day 29 and 57 respectively.

4. Feedback questionnaire can be completed within 14 days of days 28 and 56 for delayed and immediate intervention arm participants respectively.

													

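### The schedule allows the immediate arm's feedback form, and for late responders its interview, to come before the week-4 outcome questionnaires, with no matching task in the delayed arm

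*Protocol*

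**What the plan says.** Outcome questionnaires are due in both arms on Day 28 and Day 56 (Protocol Synopsis, Outline of Study; sections 5.7.3 and 5.7.5). Appendix 1, footnote 2, adds: "Participant for both arms will have a +7 days window to complete week 4 and week 8 outcome measures".

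For the feedback form and optional interview in the immediate arm, the synopsis says: "This will be completed after week 4 (Day 28) for participants in the immediate intervention arm". Section 5.7.6 likewise places both after the 4-week intervention period. The tertiary endpoint gives the form's timing as "Day 28 in the immediate intervention arm and Day 56+7 days in the delayed intervention arm", and SAP Table 2 marks it for the immediate arm at week 4 and the delayed arm at week 8. Footnote 3 of Appendix 1 covers the interview: "Optional qualitative interview for immediate and delayed intervention arm can be completed within 14 days of day 29 and 57 respectively". Footnote 4 gives the form 14 days, but with the arms the other way round: "Feedback questionnaire can be completed within 14 days of days 28 and 56 for delayed and immediate intervention arm participants respectively".

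On the form's content, section 5.7.7 says: "The first ten items assess how easy, helpful, distressing, burdensome and acceptable participants found the intervention". The form is completed in i-spero and the outcome questionnaires in ePRO (section 10.1; note to Appendix 1).

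**The concern.** The week-4 between-group comparison of secondary outcomes is the randomised one, and almost every measure in it is subjective self-report. Someone who has just rated how helpful the intervention was, or discussed it with a researcher, may answer the next questionnaires in line with that appraisal. At week 4 only the immediate arm can be in that position, so any such effect would enter the difference between arms and would not cancel.

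The protocol takes expectation seriously elsewhere: participants are not told that there are two arms. The SAP tests secondary outcomes at a two-sided 5% level without multiplicity adjustment (section 3.1), and it plans no analysis by completion order or date.

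**Working it through.** **Step 1: windows in the immediate arm, in study days.**

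- Outcome questionnaires (Appendix 1, footnote 2): 28 to 28 + 7 = 35.
- Feedback form (due Day 28; 14 days, reading footnote 4 with the arms as in its own table row): 28 to 28 + 14 = 42.
- Optional interview (footnote 3): 29 to 29 + 14 = 43.

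The form's window overlaps the outcome window on Days 28 to 35 (8 days), and the interview's on Days 29 to 35 (7 days). The delayed arm's form and interview are not due until about Day 56, so neither overlaps its week-4 outcomes.

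**Step 2: is an order required?** The synopsis and section 5.7.6 fix a point in the calendar. Neither makes submission of the outcomes a condition for opening the form or holding the interview. The form and the questionnaires sit on different platforms, and the text describes no release rule between them.

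**Step 3: which measures are exposed?** Those carrying footnote 2, from the IES-R to changes to health and work. The intrusive memory ratings carry footnote 1 (seventh day), so only a form completed the same day could precede them. The primary diary runs from Day 22 to 28; at most its last daily entry shares a date with the form, and I treat it as unaffected.

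**Step 4: scale, by assumption only.** The documents give neither the share f of the immediate arm answering out of order nor the shift s in SD units. Take 75 per arm (the planned maximum) and a baseline correlation r of 0, 0.5 or 0.7, also assumed.

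- Standard error = sqrt((2/75) × (1 − r²)) = 0.163, 0.141 or 0.117 SD.
- Bias = f × s.
- Error rate = P(|Z + bias/SE| > 1.96).
- f = 0.25, s = 0.1: bias 0.025 SD; error 5.3% (r = 0) and 5.4% to 5.5% (r = 0.5 to 0.7).
- f = 0.5, s = 0.2: bias 0.10 SD; error 9.4% (r = 0) and 10.9% to 13.8% (r = 0.5 to 0.7).

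**Step 5: room for a sequencing rule.** In the immediate arm the outcome window closes on Day 35, leaving 42 − 35 = 7 days for the form and 43 − 35 = 8 for the interview. In the delayed arm, if the +7 days for a late first session and the +7 days of footnote 2 add up, outcomes close on Day 56 + 7 + 7 = 70. A form window counted from Day 56 also ends on Day 70 (none to spare), and an interview window from Day 57 ends on Day 71 (one day). Counted from a shifted Day 63, the form window ends on Day 77 (7 days to spare). The documents do not say whether the two allowances add, and section 9.3 gives the delayed arm's form as Day 56 without the +7.

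**The case against.** The nominal plan already puts outcomes first: questionnaires on Day 28, feedback and interview after week 4. The interview is optional and can precede outcomes only for someone who answers late, volunteers and is interviewed within the same week. That stands. The realistic exposure is a short form completed on the same day, or by a late responder.

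A reader might infer that the order favours the intervention. The documents do not support that much. The form also asks about distress, burden, improvements and adverse events, and the interview covers barriers as well as acceptability. In addition, the delayed arm's first guided session (Day 29 + 7 days; section 5.7.4) overlaps its own week-4 outcome window on Days 29 to 35, so some of its pre-intervention questionnaires could follow first use and narrow the contrast. The net direction cannot be signed.

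By Day 28 the immediate arm has knowingly used the intervention for four weeks, with a guided session and repeated ratings. What one more form adds to that is unknown, and for a factual item such as sick days a shift is unlikely. Secondary outcomes are described as supportive, in a study meant to inform a later trial.

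Finally, one company manages both platforms, so release order may be set in the system build. The flow charts (protocol Appendix 2, SAP Figure 1) were not available for this check. If either source fixes the order, it only remains to state it in the text.

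**Conclusion.** The point holds as a permitted sequence, not a planned one. Nothing in the text prevents the immediate arm's form, or the interview for those using the +7-day window, from preceding its week-4 questionnaires, and the delayed arm has no counterpart at that visit. The consequence is confined to the between-group secondary comparison at week 4. The same order question arises for the delayed arm's week-8 questionnaires in its within-group comparison.

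The size is not derivable from the documents. The error rates of about 5.3% to 14% rest wholly on assumed shares, shifts and correlations, and the lower end is negligible. A reader might take the upper figure as an estimate for every outcome, but it requires half the arm to answer out of order and shift by 0.2 SD. The case for acting is that the exposure is one-sided and cheap to remove, not that a material bias has been shown.

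**What to change.** In the synopsis (Outline of Study), section 5.7.6 and Appendix 1, state that the feedback form is released and the interview held only after that participant's ePRO outcome questionnaires (week 4 in the immediate arm, week 8 in the delayed arm) have been submitted, or their +7-day window has closed.

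Two reconciliations belong with it:

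- Footnote 4 of Appendix 1 reverses the arm labels against its own table row, the tertiary endpoint and SAP Table 2. Correct the inconsistency, and confirm that the delayed arm's feedback window runs from its own shifted Day 56 + 7. Until then, spare time in that arm is not assured.
- The passages that let the delayed arm's first guided session overlap its week-4 outcome window need to be reconciled with each other.

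The cost is one sequencing rule, a release setting in i-spero, and a delay of up to 7 days for some feedback forms and interviews. Keeping completion dates would also allow the number of out-of-order questionnaires to be reported.

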## **Endpoints / Outcome Measures**

### **Primary Endpoint:**

- Number of intrusive memories of traumatic events recorded by participants in a brief daily online intrusive memory diary for 7 days during week 4 (i.e. from Day 22 to 28 post first intervention session in immediate intervention arm/equivalent timeframe in delayed intervention arm). Analysed as between-group comparison (immediate

 A 7-day window, denoted by “+7 days”, is anticipated to allow time to arrange the first intervention session with participants in the delayed intervention arm.

intervention arm vs. the delayed intervention arm) controlling for the number of intrusive memories during the run-in week.

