If on the other hand we find that the intervention is working sufficiently well when delivered by the clinical psychologists on our team (Drs [name] and [name]), we may test the intervention with different levels of researcher-guidance; for example, delivered by a less trained individual (not a qualified clinical psychologist); and with no human guidance (non-guided). We thus include the possibility to recruit and train for intervention delivery individuals who are not clinically qualified, as we have done in previous clinical studies (e.g. Kanstrup, Singh et al. 2021). Intervention delivery by less trained individuals or without human guidance would promote scalability in the future, minimising time and resources required for rapid rollout to respond to the pandemic. Decisions around when and what to optimise in the intervention will ultimately be guided by incoming participant data and feedback; consultation with our collaborators in the Intensive Care Society Expert Advisory Panel and Data Monitoring Committee; and what is clinically sensible for the target population at the time in this pandemic.

If the intervention is shown to be significantly more effective than control (assessed using Bayes factors which compare different hypotheses) before reaching the max n=150 participants, then the optimisation study may conclude early and a follow-up pragmatic RCT, testing clinical effectiveness of the optimised intervention, can be initiated (a separate ethics application will be submitted for such a study). Precise probability thresholds will be registered prior to data analysis and after consultation with [name] on our Expert Advisory Panel. Our thinking around this has been informed by initial power estimates based on an effect size of  $d= 0.63$  for the

primary outcome, pooled from three RCTs of this intervention Horsch et al, 2017; [name] et al., 2018; Kanstrup, Singh et al. 2021). Our simulations estimate approximately 84% power to find strong evidence for the intervention by the time the maximum sample size (n=150) is reached.

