## **9.0 Primary and Secondary Endpoints**

### **9.1 Primary Endpoint**

- Number of intrusive memories of traumatic events recorded by participants in a brief daily online intrusive memory diary for 7 days during week 4 (i.e. from Day 22 to 28 post first intervention session in immediate intervention arm/equivalent timeframe in delayed intervention arm). Analysed as between-group comparison (immediate intervention arm vs. the delayed intervention arm) controlling for the number of intrusive memories during the run-in week.

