## 11.2 Data Set for Analysis

All analyses will be conducted on an intention to treat (ITT) basis. The ITT is defined as all randomised participants.

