### **Definition of protocol deviations:**

A full list of protocol deviations will be denoted prior to unblinding of treatment including:

1. Non-completion of the primary outcome measure
2. Non-completion of guided intervention session/non-adherence to the intervention (as defined above).

All protocol deviations will be summarised, using the number (%) of participants by treatment group with details of type of deviation provided. The patients that are included in the ITT analysis data set will be used as the denominator to calculate the percentages. No formal statistical testing will be undertaken. Protocol deviations are classified prior to unblinding of treatment. A blinded list of protocol deviations will be shared with the statistician after the data base lock is reached.

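### The plan gives no Day 1, and so no week-4 primary window, to an immediate-arm participant who never completes the guided session

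*Protocol*

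**What the plan says.** The note on Day 1 in the Protocol Synopsis (Outline of Study), repeated in Protocol 3.2, anchors immediate-arm time to an event after randomisation: Day 1 is "defined as the day on which the participant completes the first intervention session with researcher support (guided session". Protocol 9.1 sets the primary window as "from Day 22 to 28 post first intervention session in immediate intervention arm/equivalent timeframe in delayed intervention arm", and SAP 5.1.1 does the same. The Day 28 questionnaires (Protocol 5.7.3) use the same clock. In the delayed arm, Day 1 "will be paired to the timing of Day 1 for participants in the immediate intervention arm"; how the pairing is done is not described.

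Protocol 11.2 states: "The ITT is defined as all randomised participants". SAP 3.3 agrees. SAP 3.2 foresees non-starters, listing "Non-completion of guided intervention session/non-adherence to the intervention (as defined above" as a deviation tabulated over the ITT set. SAP 3.3 removes people with significant deviations from the per-protocol set only. SAP 4.3 nevertheless has CONSORT categories for participants who did not receive their allocation and for those randomised but left out of the primary analysis. SAP 5.3 imputes missing diary counts, starting from the participant's own available diary data. SAP 5.2.3(a) makes the observed-data model a sensitivity analysis.

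**The concern.** The outcome clock in one arm starts only when the participant takes up treatment. An immediate-arm participant who never completes the guided session has, on the written rule, no Day 22-28 and no Day 28. A delayed-arm participant completes the week-4 diary before their own guided session, so an equally unengaged control can still be sent it. Missing primary outcomes can therefore depend on uptake in one arm only.

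The primary objective concerns immediate access to the intervention, so non-starters belong in the estimate. What happens to them is left to an unwritten choice, and a week-4 diary that was never sent cannot be recovered at analysis.

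**Working it through.** **Plan figures.** The documents give no non-start rate and no figure for this problem, so there is nothing to reproduce. The 84% simulated power in Protocol 11.1 does not bear on the point.

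**Is there a fallback date?**

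- The +7-day allowance for arranging the first session (Synopsis footnote) covers the delayed arm only.
- The Appendix 1 baseline window is counted relative to Day 1, so it gives a non-starter no date.
- The +7 days in Appendix 1 note 2 extends completion of the week-4 and week-8 measures; it does not create a Day 1.
- Protocol 3.1 and 5.7.3 intend week-4 collection from everyone, but give no date for someone without a Day 1.

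**What can happen to a non-starter.**

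1. Week 4 is treated as its own series. There is then nothing to impute from, and the person falls into the SAP 4.3 excluded category. The SAP 5.2.3(a) analysis also omits them.
2. Run-in counts fill week 4. Entry required at least three memories in that week (Protocol 4.2), so any later decline is erased for these people.
3. Study staff choose a date case by case. Researchers in contact with participants are unblinded (Protocol 7.1.2).

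**Assumed inputs (none is in the documents).** p = non-start share in the immediate arm, 10% or 20%. k = non-starters' week-4 count relative to starters', 0.5 to 2. r = control week-4 count relative to run-in, 0.7 to 1.0. All delayed-arm participants are taken as observed, and run-in means as equal between arms.

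**Null effect, non-starters dropped.** Rate ratio = 1/[(1-p) + pk].

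| p | k = 0.5 | k = 1.5 | k = 2 |
|---|---|---|---|
| 10% | 1/0.95 = 1.05 | 1/1.05 = 0.95 | 1/1.10 = 0.91 |
| 20% | 1/0.90 = 1.11 | 1/1.10 = 0.91 | 1/1.20 = 0.83 |

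**Null effect, non-starters imputed at run-in level.** Take k = 1 and r = 0.7. Rate ratio = (1-p) + p/r.

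- p = 10%: 0.90 + 0.10/0.7 = 1.04
- p = 20%: 0.80 + 0.20/0.7 = 1.09

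**A real effect (assumed).** Starters have ratio 0.50, non-starters 1.0, with k = 1. The ratio for offering access is 0.5(1-p) + p. If imputed at run-in level it is 0.5(1-p) + p/r.

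| p | All observed | Dropped | Imputed, r = 1.0 | Imputed, r = 0.7 |
|---|---|---|---|---|
| 10% | 0.45 + 0.10 = 0.55 | 0.50 | 0.55 | 0.45 + 0.143 = 0.59 |
| 20% | 0.40 + 0.20 = 0.60 | 0.50 | 0.60 | 0.40 + 0.286 = 0.69 |

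The same non-starters can make the intervention look better or worse, depending on handling that the plan does not state.

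**Power cost of observing everyone.** With 75 per arm, d = 0.63 and a fixed-sample two-sided 5% comparison of means, power is 97.1%. If non-starters gain nothing, d becomes 0.63 × 0.9 = 0.567 (power 93.5%) or 0.63 × 0.8 = 0.504 (power 87.0%). This simplifies the trial's sequential Bayesian design and only shows the scale of the cost.

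**The case against.** A reader might infer that the ITT comparison cannot be made, and that the trial must compare immediate-arm starters with everyone in the delayed arm. The documents do not support that. SAP 5.3 imputes missing diary counts, every randomised participant has a run-in diary, and the observed-data model is only a sensitivity analysis. An all-randomised analysis can be run. What remains is that a non-starter's whole week 4 would rest on pre-randomisation counts, and SAP 5.3 does not clearly say how a wholly missing week is handled.

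A reader might also infer that the bias favours the intervention. That needs non-starters to be dropped and to have higher counts. With lower counts, or with run-in imputation while controls decline, it runs the other way.

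Nor do the documents show that every delayed-arm participant has a window. The pairing method is not given; if it is one-to-one, a control paired to a non-starter could also lack a Day 1.

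Three further defences have some weight. The protocol intends the week-4 diary for everyone; that shows intent but supplies no date. This is an optimisation study informing a later trial, which lowers the stakes without closing the gap. Delivery "and with no human guidance (non-guided" is only a possibility in Protocol 3.2, with changes decided by the Data Monitoring Committee (Protocol 13.0). It is a reason to write a definition that would survive the change, not a present defect.

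**Conclusion.** The gap is real. Immediate-arm non-starters are in the ITT population with no defined week-4 collection date, so followed as written their primary outcome is either left out or imputed from run-in data. The size and direction of the bias are unknown. The illustrated null ratios run from 0.83 to 1.11 if non-starters are dropped and from 1.04 to 1.09 if they are imputed at run-in level. Both ranges rest on the assumed 10-20% non-start and the assumed values of k and r. If nearly everyone starts, the effect is small. The case for acting is that the missing diaries can be obtained only during the trial and the remedy is cheap.

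**What to change.** In Protocol 3.2 and 9.1 and SAP 5.1.1:

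- **Assigned Day 1.** An immediate-arm participant with no completed guided session by a fixed number of days after randomisation is assigned Day 1 by the randomisation-based interval used to pair the delayed arm, for example the running immediate-arm median from randomisation to session. The cut-off must fall before the assigned Day 22, that is, within 21 days of the assigned Day 1, so that the diary can still be sent on time.
- **Late starters.** They keep the assigned Day 1 for outcome timing.
- **Collection.** ePRO sends the Day 22-28 diary and Day 28 questionnaires whether or not the session took place, and observed data enter the ITT analysis.
- **Pairing.** State the rule so that no delayed-arm participant's Day 1 depends on one individual's start.
- **Non-guided delivery, if used.** Set Day 1 by the assigned interval. First access would again depend on engagement.
- **Reconciliation.** Align SAP 4.3 and 5.3 with the ITT definition, and say how a wholly missing week 4 is handled.

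The cost is a few sentences and an ePRO trigger that does not wait for the session. This changes outcome timing only, not treatment. The estimated effect may be somewhat smaller because non-starters are included, and some assigned diaries will still be missing and need imputation.
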